16.2 Study Endpoints

A. Long-Term Effectiveness (Primary effectiveness endpoint)

Two endpoints will be used for long term effectiveness after the initial AF ablation procedure (only):

Single Procedure Freedom from AF/AT recurrence* at 3 months, and

Single Procedure Freedom from AF/AT recurrence* from 3-12 months after the initial AF ablation procedure.

Freedom from AF/AT recurrence is defined as no documented episodes of AF > 30 seconds with conventional non-invasive monitoring. In the case of a cardiac implanted electronic device (CIED), freedom from AF/AT recurrence is defined as no documented episodes of AF > 30 in a 48 to 72-hour window at the follow-up visits in addition to any symptomatic episodes with documented AF > 30 seconds. AT recurrence does not include episodes of CTI (cavotricuspid isthmus) dependent flutter.

The statistical hypothesis for this endpoint is operationalized as follows:

$H_0: p_E = p_C$

$H_A: p_E \neq p_C$

$\alpha =$ [REDACTED]

Where:

p_E = the proportion of "successes" in the FIRM arm

p_C = the proportion of "successes" in the conventional ablation control arm

The proportion of successes in each treatment arm shall be evaluated relative to their respective primary endpoint using both Chi-Square (Binomial, 1df) and by Kaplan-Meier survival estimation. Each evaluation will include 95% confidence intervals. Since there are multiple (dual) independent endpoints, each resulting p-value will be reported both as calculated, and the associated Hochberg corrected p-value.

B. Acute Effectiveness (Secondary effectiveness endpoint)

The acute success of FIRM-guided procedure is defined as elimination of the source of arrhythmias identified by FIRMap as indicated by;

1. No evidence of the source on FIRMap immediately post-procedure, OR
2. Reduction of electrogram amplitude to <0.2mV in region designated by FIRMap

The proportion of successes in each arm will be calculated as follows:

$$\frac{n}{N}$$

Where:

n = the total count of "successful" subjects in the arm in question

N = the total count of subjects for that arm in the ITT group

The statistical hypothesis for this endpoint is operationalized as follows:

$$H_0: p_E = p_C$$

$$H_A: p_E \neq p_C$$

$$\alpha = \text{[REDACTED]}$$

Where:

p_E = the proportion of "successes" in the FIRM arm

p_C = the proportion of "successes" in the conventional ablation control arm

This endpoint will be evaluated using a Chi-Square test of independence, the proportions assumed to be binomial for each group.

C. Acute Safety (Primary safety endpoint)

The acute safety success of either treatment arm is defined as freedom from serious adverse events related to the procedure within ten (10) days of the index procedure. The proportion of successes in each arm will be calculated as follows:

$$\frac{n}{N}$$

Where:

n = the total count of subjects presenting freedom from serious adverse events related to the procedure within ten (10) days of the index procedure.

N = the total count of subjects in that arm in the ITT group

The statistical hypothesis for this endpoint is operationalized as follows:

$H_0: p_E = p_C$

$H_A: p_E \neq p_C$

Where:

p_E = the proportion of "successes" in the FIRM arm

p_C = the proportion of "successes" in the conventional ablation control arm

This endpoint will be evaluated using a Chi-Square test of independence, the proportions assumed to be binomial for each group.

D. Long-Term Safety (Primary safety endpoint)

Long-term safety is defined as freedom from procedure-related serious adverse events (SAEs) (including those related to repeat procedures) within one year of the initial procedure.

The statistical hypothesis for this endpoint is operationalized as follows:

$H_0: p_E = p_C$

$H_A: p_E \neq p_C$

$\alpha =$

Where:

p_E = the proportion of subjects free from serious adverse events related to the procedure (including from any repeat procedures required) within one year of the index procedure in the FIRM arm

p_C = the proportion of subjects free from serious adverse events related to the procedure (including from any repeat procedures required) within one year of the index procedure in the conventional ablation control arm

The proportion of events in each treatment arm shall be evaluated relative to their respective primary endpoint using both Chi-Square (Binomial, 1df) and by Kaplan-Meier survival estimation. Each evaluation will include 95% confidence intervals.

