Freedom from AF/AT recurrence is defined as no documented episodes of AF > 30 seconds with conventional non-invasive monitoring. In the case of a cardiac implanted electronic device (CIED), freedom from AF/AT recurrence is defined as no documented episodes of AF > 30 seconds in a 48 to 72-hour window at the follow-up visits in addition to any symptomatic episodes with documented AF > 30 seconds. AT recurrence does not include episodes of CTI (cavotricuspid isthmus) dependent flutter.

Refer to the Statistical Analysis Plan for details.

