7.2 PRIMARY EFFECTIVENESS ENDPOINTS

Effectiveness endpoints are defined in the table below.

Table 2 – Primary Effectiveness Endpoints

Endpoint	Definition
Long term success	
Dual endpoints will be used for long term effectiveness after the initial AF ablation procedure (only):
 
(1) Single Procedure Freedom from AF/AT recurrence* at 3 months, or
 
(2) Single Procedure Freedom from AF/AT recurrence* from 3-12 months after the initial AF ablation procedure.
 
* Freedom from AF/AT recurrence is defined as no documented episodes of AF > 30 seconds with conventional non-invasive monitoring. In the case of a cardiac implanted electronic device (CIED), freedom from AF/AT recurrence is defined as no documented episodes of AF > 30 seconds in a 48 to 72-hour window at the follow-up visits in addition to any symptomatic episodes with documented AF > 30 seconds. AT recurrence does not include episodes of CTI (cavotricuspid isthmus) dependent flutter.

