7.3 SECONDARY ENDPOINTS

Secondary endpoints are defined in Table 3 below. This study will also collect data relating to the health economics of the FIRM-guided procedure to conduct additional evaluations if primary endpoints are met.

Table 3 – Secondary Endpoints

Endpoint	Definition
Acute Effectiveness	
The acute success of FIRM-guided procedure is defined as elimination of the source of arrhythmias identified by FIRMap as indicated by;
 
 1. No evidence of the source on FIRMap immediately post-procedure, OR 2. Reduction of electrogram amplitude to <0.2mV in region designated by FIRMap

Table 4 – Additional Evaluations

Parameter	Definition
Total RF ablation time	Total RF ablation time as measured by total time of ablation lesion applications, from first ablation lesion to end of last lesion, will be documented. These values will be compared between the FIRM-guided and conventional ablation groups. If ablation for AT/atrial flutter is pursued, this ablation time will be documented separately
Repeat procedure and hospitalization	Any descriptive information regarding repeat procedures and re-hospitalizations will be compared between groups
Cumulative long-term freedom from AF	Cumulative long-term freedom from AF will be assessed at 12 months after the initial AF procedure but will permit results of repeat ablation
Cumulative long-term freedom from AF without use of anti-arrhythmic drugs	Cumulative long-term freedom from AF without use of anti-arrhythmic drugs will be assessed at 12 months after the initial AF procedure but will permit results of repeat ablation
Early Recurrence of AF/AT	Recurrences of sustained AF/AT in the first 3 months (blanking period).
Change in Atrial Function	Change in left atrial size and pulmonary vein inflow Doppler on echocardiogram (when available)
Change in Ventricular Function	Change in left ventricular ejection fraction and parameters of diastolic dysfunction (when available)
Quality of Life	Impact on quality of life, using patient-reported outcome instruments (EQ-5D and AFEQT), within treatment groups (change from pre-procedure to post-procedure follow-up timepoints) and between treatment groups. Analysis will be performed if primary endpoints are met.
Economic Analysis	Cost-effectiveness analysis based on clinical and patient-reported outcomes and resource utilization. Analysis will be performed if primary endpoints are met.

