3-D Electroanatomic Mapping	3-D electroanatomic maps may be created using CARTO (Biosense Webster, Johnson & Johnson) or Nav-X (St. Jude Medical) systems for documentation of anatomy and ablation lesion locations.
Induction of sustained AF	If the patient is not experiencing spontaneous, sustained AF (>5 min uninterrupted), induce sustained AF by atrial burst pacing, typically from the coronary sinus, with or without isoproterenol infusion in conventional clinical fashion. IF AF CANNOT BE SUSTAINED, THE PATIENT DOES NOT MEET THE INCLUSION CRITERIA FOR THE PROTOCOL AND THE PATIENT WILL UNDERGO CONVENTIONAL AF ABLATION PER PHYSICIAN DISCRETION.

Ablation data	For each ablation, the following data will be recorded: time, catheter size, lesion number, phrenic nerve assessment (if in an area of potential phrenic nerve proximity), approximate catheter tip location, duration of application, average temperature, and any comments.
FIRM-guided procedure	Under fluoroscopic guidance, a cardiac ablation catheter is passed to the location(s) identified as AF source rhythms (rotors or focal impulses). Therapy can be applied at up to 6 sites identified by the initial or repeated FIRMap per standard practice.
Conventional Ablation	Conventional ablation typically consists of isolation of all four pulmonary veins per guidelines. In addition, in the conventional arm of the study, data will be recorded regarding any additional ablation such as that performed per local routine for AF (e.g. CFAE, roof line, additional trigger elimination, etc.). Such additional ablation is NOT typically performed in the FIRM-guided limb where only PVI is typically performed for the purposes of AF ablation beyond FIRM-guided locations.
Additional ablation for other arrhythmias (non-AF)	Additional ablation for other arrhythmias will be noted for atrial tachycardia (AT) and/or right cavo-tricuspid isthmus ablation in the event that the patient has documented AT/atrial flutter prior to or during the procedure.
Electrograms	Electrogram recordings evaluating conduction into or out of each treated vein.

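### The primary effectiveness endpoint is named freedom from AF/AT recurrence, but every clause that defines failure counts AF only

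*Protocol*

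**What the plan says.** The synopsis (Section 3) spells the long-term effectiveness endpoint out as freedom from recurrence of both atrial fibrillation and atrial tachycardia. Section 7.2 (Table 2) and Section 16.2 A use the short form AF/AT. All three places then define it: "Freedom from AF/AT recurrence is defined as no documented episodes of AF > 30 seconds with conventional non-invasive monitoring".

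For subjects with a CIED there are two further clauses, one for a window around each visit and one for symptomatic episodes. Both refer to AF alone. In Section 16.2 A the window clause has also lost its time unit: "no documented episodes of AF > 30 in a 48 to 72-hour window at the follow-up visits". The synopsis and Table 2 give seconds there.

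Each copy closes with an exclusion: "AT recurrence does not include episodes of CTI (cavotricuspid isthmus) dependent flutter". The synopsis adds "Refer to the Statistical Analysis Plan for details".

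One other rule bears on scoring. Under Recurrence of AF, Section 10.3 makes a subject who needs re-ablation for AF a primary efficacy failure. It does not mention re-ablation for AT.

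**The concern.** The name and the flutter exclusion say that AT is part of the endpoint. The clauses that decide success or failure leave it out. No sentence makes an AT episode a failure, and none gives AT a minimum duration.

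This variable is the success count in the primary comparison of proportions, the event in the Kaplan-Meier estimate and the subject of the interim analysis (Sections 16.2 A and 16.3). With two readings available, sites and adjudicators can score the same subject differently. A choice between the readings made after data have accrued would leave the primary event definition open to influence from the results.

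**Working it through.** **Text comparison**

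| Element | Section 3 | Section 7.2, Table 2 | Section 16.2 A |
|---|---|---|---|
| Endpoint name | AF and AT | AF/AT | AF/AT |
| Non-invasive monitoring | AF > 30 s | AF > 30 s | AF > 30 s |
| CIED window at visits | AF > 30 s | AF > 30 s | AF > 30, unit missing |
| CIED symptomatic episodes | AF > 30 s | AF > 30 s | AF > 30 s |
| Excluded from AT recurrence | CTI-dependent flutter | CTI-dependent flutter | CTI-dependent flutter |
| Clause making AT a failure | none | none | none |

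Three copies with three operative clauses each give nine clauses, and all nine count only AF.

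**Can AF be read as shorthand for AF/AT?** The protocol's usage is against it.

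- Table 4 measures early recurrence with both rhythms: "Recurrences of sustained AF/AT in the first 3 months (blanking period").
- The same table frames a later measure with AF alone: "Cumulative long-term freedom from AF will be assessed at 12 months after the initial AF procedure but will permit results of repeat ablation".
- Table 6 treats AT as a non-AF arrhythmia: "Additional ablation for other arrhythmias will be noted for atrial tachycardia (AT) and/or right cavo-tricuspid isthmus ablation".

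**Consequence for one subject.** Take a documented non-CTI AT episode of any length and no AF. By the operative clauses the subject is a success. By the endpoint name, and by what the flutter exclusion implies, the subject is a failure.

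**Scale, for illustration only.** There is no figure in the plan to reproduce: alpha and the sample-size section (16.4) are redacted, and no AT rate is given. Assumed inputs, not tied to either of the two dual endpoints:

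- AF/AT recurrence R = 30-50%
- share of recurrences that are AT only, s = 10-30%

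Inputs from the protocol: up to 350 subjects randomized 1:1 (Section 6.1), so 350 / 2 = 175 per arm; interim analysis at 100 per arm (Section 16.3).

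Overstatement of success per arm under the literal reading = R × s:

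- low: 0.30 × 0.10 = 3 points
- middle: 0.40 × 0.20 = 8 points
- high: 0.50 × 0.30 = 15 points

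In subjects per arm:

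- full enrolment: 0.03 × 175 = 5.25 to 0.15 × 175 = 26.25, about 5 to 26
- interim: 0.03 × 100 = 3 to 0.15 × 100 = 15

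Effect on the comparison: literal success equals AF/AT success plus the AT-only rate in each arm. The FIRM-minus-control difference therefore shifts by the AT-only rate in FIRM minus the AT-only rate in control.

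- Equal AT-only rates: shift 0.
- Equal R, s = 10% in FIRM and 20% in control: R × (0.10 − 0.20) = −3, −4 and −5 points at R = 30%, 40% and 50%.
- Shares reversed: +3, +4 and +5 points.

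Table 6 gives no basis for choosing a direction. The conventional arm may receive extra AF lesions (of the FIRM arm it says "Such additional ablation is NOT typically performed in the FIRM-guided limb where only PVI is typically performed"), while the FIRM arm may be treated at up to six mapped sites as well as receiving PVI.

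**The case against.** The strongest reply is that only one reading gives every sentence a function. The synopsis names AT outright and the flutter exclusion is empty unless other AT counts, so the operative clauses have probably just lost their AT term. That is a fair view of the intent, and it supports the fix. It does not change what the clauses say, and it leaves AT without a duration.

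Second, the synopsis defers detail to the SAP, and Section 13.5 gives the DMC ongoing adjudication of endpoint events. Either could limit mis-scoring in practice, and the SAP was not available. But this is not a detail left open. The protocol states the definition in full three times, and each copy conflicts with itself. An SAP that counts AT departs from the operative clauses; one that counts only AF departs from the name and voids the flutter sentence. Adjudicators also need one rule to apply.

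Third, Section 10.3 adds a second route to failure, so an AF episode over 30 seconds is not the only one. That is correct, but this route is also limited to AF. Its silence on AT re-ablation is not itself a contradiction.

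Fourth, the numbers rest on assumptions. That stands. They show scale and are not evidence of bias. The 175 per arm is also a ceiling, because enrolment is up to 350 and Section 16.1 limits the analysis set to eligible subjects who had a catheter inserted.

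Fifth, no passage sets 30 seconds for AT. That is true, but it is the only episode threshold in a definition headed AF/AT. The sponsor should confirm it.

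**Conclusion.** The concern holds and must be fixed. The contradiction is in the current text of all three copies, and neither redaction nor PDF extraction explains it. It does not depend on any assumed number.

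On the assumed inputs, the choice of reading moves reported success by 3-15 points in each arm. The difference between arms is unaffected if AT-only rates are equal. It shifts by 3-5 points, in either direction, if the AT-only share differs by an assumed 10 percentage points. The protocol does not allow the direction to be inferred, and no statement about type I error or power is made because alpha is redacted.

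**What to change.** In Sections 3, 7.2 (Table 2) and 16.2 A, replace the event in each of the three monitoring clauses with: *no documented episode of AF or AT (excluding CTI-dependent flutter) lasting > 30 seconds*. This matches the endpoint name, gives the flutter sentence its effect and restores the unit missing from the CIED window clause in Section 16.2 A. Align the endpoint-failure rule in Section 10.3 with the same definition. That concerns scoring only and does not touch when re-ablation is done. Report AF-only freedom as a supportive analysis, so that the effect of counting AT is visible.

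If the sponsor meant AF only, the name and the flutter sentence must change instead. One of the two has to give way.

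The cost is wording in four places, matching case report form and adjudication text, and stated success rates that are somewhat lower in both arms. The sponsor should also confirm that the rates behind the redacted Section 16.4 used the same definition.

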4 BACKGROUND AND RATIONALE

Atrial fibrillation (AF) is the most common sustained arrhythmia in man, and has an increasing population prevalence over time. Treatment is aimed at stroke prevention on the one hand, and amelioration of symptoms (palpitations, lightheadedness, dyspnea, fatigue) due to the arrhythmia. Medical therapy often fails to render a satisfactory response for the latter, prompting the search for alternative therapies. Surgical and, in the last 15 years, catheter ablation techniques have been devised to try to prevent episodes from starting. Groundbreaking work by Haïssaguerre¹ showed that premature discharges or rapid repeated firing from the pulmonary veins (PVs) could trigger AF episodes and that electrical isolation of the PVs could potentially cure the patient of AF. PV isolation currently is a painstaking process consisting of delivering radiofrequency energy in the left atrium to isolate these veins. Such procedures take 3-5 hrs. to complete depending on the complexity of the individual case, and a majority of patients require a 2nd or even 3rd procedure to achieve acceptable antiarrhythmic results. Despite considerable investigative effort, the exact pathophysiology of how PV triggers initiate and or maintain episodes of AF has been elusive.

Recently, Narayan et al² have developed an algorithm that has been licensed for use with a novel mapping technology (RhythmView, Abbott (Topera, Inc.), Menlo Park, CA) for analyzing atrial recordings during human AF, finding that >95% of cases demonstrate either a rapidly spinning rotor (small circuit) or very rapid focal impulse formation. Furthermore, they have shown that catheter ablation at these relatively circumscribed areas can significantly affect AF, either by substantial slowing of the rate or termination (to an atrial tachycardia or sinus rhythm). In the CONFIRM (CONventional vs Focal Impulse and Rotor Modulation) trial, patients were treated with either conventional mapping and ablation (largely PV isolation or PVI) vs ablation of rotors or sites of focal impulse formation as designated by the mapping algorithm, followed by conventional ablation (PVI). The authors found much higher acute and long-term efficacy when focal impulse and rotor modulation (FIRM procedure) was used (82.4 vs 44% freedom from AF at 24 months post procedure). Although CONFIRM was a controlled study, a randomized evaluation would be warranted.

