6.1 SAMPLE SIZE

A total of up to 350 subjects at up to 25 investigative sites will be enrolled and equally (1:1) randomized between those undergoing conventional AF treatment with ablation, vs. those with FIRM-guided procedures followed by conventional AF ablation. Additionally, ablation of any atrial tachycardias (AT) and/or the cavitricuspid isthmus may be performed in those subjects with documented AT/atrial flutter.

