6.2 RANDOMIZATION

Block randomization using a web-based database system will be used to assign subjects (1:1) to the conventional AF ablation treatment without FIRM-guided diagnostic procedure, or to the FIRM-guided procedure followed by conventional AF ablation.

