8 SELECTION, DISCONTINUATION, AND WITHDRAWAL OF SUBJECTS

8.1 SELECTION CRITERIA

The criteria listed below shall be used to determine if a participant is eligible for entry into the study. A subject must meet ALL of the study inclusion criteria and NONE of the study exclusion criteria in order to be considered eligible for participation.

A. *Inclusion Criteria*

Subjects are required to meet the following inclusion criteria:

1. Male or female 18 – 80 years of age.
2. Experiencing at least two (2) documented episodes of persistent atrial fibrillation (including long standing persistent) during the 3 months preceding study entry with clinical indication for AF ablation per guidelines. At least one episode should be documented by rhythm strip or ECG. Persistent AF is defined as continuous AF that is sustained beyond seven days (long standing persistent is >12 months). Episodes of AF in which a decision is made to electrically or pharmacologically cardiovert the patient after ≥48 hours of AF, but prior to 7 days, should also be classified as persistent AF episodes.
3. Refractory, contraindicated, or intolerant to Class I or III anti-arrhythmic medications. Drug doses must be therapeutic and stable.
4. Novel Oral Anticoagulant (e.g. dabigatran, rivaroxaban, apixaban), Warfarin (therapeutic INR ≥ 2.0 for at least three weeks prior to randomization), or other similar standard-of-care oral anticoagulant therapy is required (aspirin is not considered similar) for those subjects who meet two or more of the following criteria:
 - a. Age 65 years or older
 - b. Diabetes
 - c. Coronary artery disease (CAD)
 - d. Congestive heart failure
 - e. Hypertension with systolic >165 mm Hg
5. Willingness and able to remain on anti-coagulation therapy for a minimum of 3 months post procedure for all subjects and at least 12 months post procedure if the patient is on anti-coagulation pre-procedure or has CHADS2 score ≥ 2.
6. Left atrial diameter < 6.0 cm via transthoracic echo; or <6.5 cm via CT or MRI up to 3 months pre-procedure with documented image of largest dimension, or intraprocedural ICE or atrial angiogram if CT/MRI not available.
7. Sustained AF (>5 min uninterrupted) during the electrophysiology procedure. If the subject is not experiencing spontaneous, sustained AF, it may be induced by burst pacing (typically from the coronary sinus) with or without isoproterenol infusion in conventional clinical fashion.

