10.1 SCREENING AND BASELINE

A. *Screening*

Patients at the investigational sites with persistent AF will be asked about their interest in study participation. For those patients who express an interest to participate, the inclusion/exclusion criteria will be reviewed against existing medical history and the results of any standard clinical work-up to assess preliminary eligibility. Potential patients who do not meet entrance criteria may, as appropriate, repeat screening evaluations at a later time for possible enrollment into the study.

B. *Baseline Assessment*

If the patient is not excluded on the basis of existing medical history and standard clinical work-up, the patient will be asked to provide informed consent to participate in the study. Baseline assessments include the following as shown in Table 5 – Schedule of Assessments.

- Determine study eligibility based on the requirements specified in the inclusion / exclusion criteria.
- Demographics.
- Medical history, including any hospitalizations or emergency room visits for episodes of all cardiac arrhythmias within six months of screening, all anti-arrhythmic drugs (AADs) and other cardiac medications.
- Reported incidence of at least two (2) documented episodes of persistent atrial fibrillation (AF) during the three months preceding trial entry (at least one episode should be documented by rhythm strip or ECG).
- Treatments administered for atrial fibrillation in the six months prior to enrollment, e.g., pharmacologic treatments and non-pharmacologic interventions. Medications should include dose and duration.
- Documentation of therapeutic International Normalization Ratio (INR) for three weeks prior to the procedure (if applicable per Inclusion Criteria) in cases of subjects taking warfarin.
- NYHA class.
- Current cardiac rhythm.
- Largest dimension left atrial diameter measured from transthoracic echo, cardiac CT or cardiac MR within the last 3 months with image documentation. Intracardiac echocardiographic measurement at the time of the procedure can alternatively be used to document this.
- Ejection fraction (EF) measured within the last 3 months or from the pre-procedure TEE or TTE.
- When clinically indicated, TEE will be performed within 72 hours prior to the ablation procedure. If any evidence of left atrial thrombus is discovered, then the ablation procedure will not be performed at that

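### The primary effectiveness test is valid but unadjusted; adjusting for left atrial diameter and AF type would give a small, optional gain in precision

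*Protocol*

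**What the plan says.** Section 16.2 A sets the null hypothesis p_E = p_C against a two-sided alternative for each of two endpoints: single-procedure freedom from AF/AT recurrence at 3 months, and from 3 to 12 months. The proportions are evaluated "using both Chi-Square (Binomial, 1df) and by Kaplan-Meier survival estimation", with 95% confidence intervals and Hochberg-corrected p-values. No baseline covariate is named.

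Section 6.2 describes the allocation: "Block randomization using a web-based database system will be used to assign subjects (1:1". It gives blocks but no stratification factor. Section 6.1 sets the size: "A total of up to 350 subjects at up to 25 investigative sites will be enrolled and equally (1:1) randomized".

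Two baseline characteristics stand out in the protocol's own text.

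- **Left atrial diameter.** Section 8.1 caps it for entry at below 6.0 cm by transthoracic echo or below 6.5 cm by CT or MRI. Section 10.1 B lists it at baseline: "Largest dimension left atrial diameter measured from transthoracic echo, cardiac CT or cardiac MR within the last 3 months". Both sections also accept a measurement made during the procedure: intracardiac echo in both, and an atrial angiogram as well in section 8.1.
- **AF type.** Section 8.1 admits both persistent and long-standing persistent AF and gives the boundary: "long standing persistent is >12 months". Neither Table 5 nor the baseline list in section 10.1 has a separate item for AF type. Medical history, cardiac diagnosis and documentation of AF are listed.

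**The concern.** The population is mixed on two characteristics that the protocol itself singles out. As written, neither the allocation nor the primary analysis takes account of them. If either predicts recurrence, an unadjusted comparison carries outcome variation that a model could remove, and a chance imbalance between arms stays in the point estimate.

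What is at stake is precision only: a somewhat wider confidence interval and somewhat lower power than the same subjects could give. Because section 16.2 A states the test, an adjusted primary analysis would need that text to change.

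**Working it through.** **Inputs from the protocol.** Up to 350 subjects, 1:1, so at most 175 per arm (section 6.1). Two-sided test, two endpoints, Hochberg (section 16.2 A).

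**Inputs that must be assumed.** Alpha, power and planning rates are blacked out, so the sample size cannot be reproduced. I take two-sided 0.05 and 60% versus 75% freedom from recurrence. The share of outcome variance explained by the covariates, R2, is not in the protocol and is varied.

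**Step 1: power of the unadjusted test.** With mean proportion 0.675:

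Power = Φ{ [d√n − z√(2p̄(1−p̄))] / √(p1(1−p1) + p2(1−p2)) }

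- d√n = 0.15 × √175 = 1.984
- z√(2p̄(1−p̄)) = 1.960 × √0.43875 = 1.298
- denominator = √(0.24 + 0.1875) = 0.654
- Power = Φ(0.686 / 0.654) = Φ(1.049) = 85.3%

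**Step 2: gain from adjustment.** Approximate the adjusted analysis by an effective size per arm of 175/(1−R2). The standard error shrinks by the factor √(1−R2). The 0.025 column uses z = 2.241 and is the stricter Hochberg step.

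| R2 | Effective n per arm | SE reduction | Equivalent extra subjects on 350 | Power at 0.05 | Power at 0.025 |
|---|---|---|---|---|---|
| 0 | 175 | none | 0 | 85.3% | 77.8% |
| 0.01 | 177 | 0.5% | 4 | 85.6% | 78.2% |
| 0.02 | 179 | 1.0% | 7 | 86.0% | 78.7% |
| 0.05 | 184 | 2.5% | 18 | 87.0% | 80.0% |
| 0.10 | 194 | 5.1% | 39 | 88.8% | 82.3% |

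For example, at R2 = 0.05: 175/0.95 = 184.2, 0.15 × √184.2 = 2.036, and (2.036 − 1.298)/0.654 = 1.128, so power is 87.0%.

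With the same 15-point difference and R2 from 0.01 to 0.10, power at 0.05 goes from 81.3% to 81.7%–85.2% for a control rate of 50%, and from 92.3% to 92.5%–94.6% for 70%.

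**Step 3: what R2 might be.** R2 = Var(p)/[p̄(1−p̄)], simulated at 60% overall success for assumed odds ratios per SD of left atrial diameter and for long-standing AF, with long-standing AF in 10% or 30% of subjects.

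| Odds ratio per SD / for AF type | R2 (10%, 30%) | Power at 0.05 (10%, 30%) |
|---|---|---|
| 1.2 / 1.5 | 0.011, 0.016 | 85.7%, 85.9% |
| 1.35 / 2.0 | 0.031, 0.044 | 86.4%, 86.8% |
| 1.5 / 2.5 | 0.053, 0.074 | 87.1%, 87.9% |
| 2.0 / 3.0 | 0.114, 0.138 | 89.2%, 90.0% |

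The first three rows gain 0.4 to 2.6 power points. The last row, which needs strong predictors, gains about 4 to 5.

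**Step 4: validity of the present test.** In 10,000 simulated null trials with 175 per arm, odds ratios of 1.5 per SD and 2.5 for AF type (30% prevalence) and an overall success rate of 61%, the unadjusted chi-square rejected in 5.1%. The Monte Carlo standard error is √(0.05 × 0.95/10,000) = 0.2 points, so this agrees with 5%.

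**The case against.** The strongest reply is that nothing here is wrong. The null hypothesis concerns two marginal proportions, and a 1-df chi-square tests exactly that. Chance imbalance is already allowed for in its error rate. No stratification factor is named, so the test ignores no stratified design. The documents show no prognostic strength: a cap on atrial size at entry does not prove that size predicts recurrence within the eligible range. All of this stands, and it is why the point is optional.

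A second reply is that covariates belong to the statistical analysis plan, to which the synopsis refers for details. Adjusted analyses may well be there. But section 16.2 A does not leave the primary method open, and a general pointer for details does not replace a stated test.

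A third reply concerns the covariates. A reader might infer that left atrial diameter and AF type are known for every subject at baseline. The protocol does not support that. Sections 8.1 and 10.1 B let the diameter be first documented during the procedure, while section 8.4 places randomization after screening. A value obtained after randomization, by an operator who must know the arm to deliver it, is not a safe covariate. Echo and CT/MRI have different limits, so their readings are not one uniform scale. AF type has no item of its own. This objection stands and shapes the fix.

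A last reply is that a logistic model reports a conditional odds ratio, which is a different quantity. Standardizing to a marginal risk difference answers it. A Cox model would not, because it targets a hazard ratio and not the stated proportions.

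**Conclusion.** The primary comparison in section 16.2 A is unadjusted and valid. A standardized adjusted risk difference would keep p_E - p_C as the target and normally gain some precision, with no extra subjects or procedures. The size is small: about 0.4 to 2.6 power points under modest assumed odds ratios and about 4 to 5 under strong ones. This rests on assumed rates of 60% and 75%, an assumed alpha, an assumed R2, and a full 175 per arm. The last is an upper limit, because section 6.1 says up to 350 and section 16.1 counts only randomized subjects who met all criteria and had a catheter inserted.

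Two stronger readings are tempting. One is that the plan gives up precision for nothing; the gain is unproven, since it depends on a prognostic strength that the protocol does not give, and the change has a small cost. The other is that the unadjusted test is biased or inflates error; Step 4 shows no sign of it. The point is an optional efficiency gain and ranks below changes that should be made.

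**What to change.** Amend section 16.2 A before any unblinded look, including the interim analysis in section 16.3.

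- **Primary estimate.** For each of the two endpoints, fit a logistic model with arm, left atrial diameter, persistent versus long-standing persistent AF, and any factor used to block randomization. Predict every subject's outcome under each arm, average, and report the difference as the estimate of p_E - p_C with a 95% confidence interval. Apply Hochberg to the two resulting p-values.
- **Covariate rules.** Use only values recorded before randomization. Add an indicator for measurement method (transthoracic echo versus CT/MRI). Where left atrial size was first obtained during the procedure, treat the baseline value as missing and use a missing-value indicator. Derive AF type from the AF history using the 12-month boundary in section 8.1.
- **Sensitivity analysis.** Keep the unadjusted chi-square.

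The cost is one derived field for AF type, a check that the AF history records enough to derive it, and slightly more analysis work. If sites turn out to be the blocking factor, 350 subjects over 25 sites is 14 per site on average, so a rule for pooling small sites would be needed.
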